10.4 Participant Retention and Follow-up

Participants in the intervention arm will be advised that low vision training is required to fully adapt to the device. Participants in the control group will be attending low vision training which is in addition to their usual standard of care.

Participants who do not attend follow up visits will be contacted to determine if they still consent to remain in the study and permission will be sought for use of data collected to date.

10.5 Data Management

Trial data, including the CRF and questionnaires, will be entered onto a web-based Clinical Trial Database (MACRO) by CTU personnel and processed electronically as per CTU Standard Operating Procedures (SOPs) and the study specific Data Management Plan (DMP). Data queries will be 'raised' electronically. Where clarification from site staff is required for data validations or missing data, site staff will respond to email queries to enable amendments, where applicable, to be made to the Clinical Trial Database.

Ophthalmic images will be anonymised and uploaded electronically by the PI or designee at site to the Central Angiographic Resource Facility (CARF). CARF is only accessible by a username/password combination unique to the site. Once uploaded, the images will be downloaded by CARF personnel and stored on secure servers housed by Queen's University Belfast.

All essential documentation and trial records will be stored securely and access will be restricted to authorised personnel. All study documentation (including participant medical records) and data will be archived as per regulatory requirements and those responsible for archiving will be noted on the sponsor delegation framework.

10.6 Data Analysis

10.6.1 Analysis population

In the efficacy evaluation, the primary analysis will be conducted on an intention to treat basis, that is, on all outcome data obtained from all participants as randomised and regardless of protocol

adherence. Per-protocol analysis will also be conducted which will involve a comparison of treatment groups that includes only those participants who completed the treatment originally allocated. In the mechanistic evaluation, the analysis will be performed only on the subjects who were randomised to the intervention arm and who received the treatment originally allocated.

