8.3 Interventions

The planned interventions will be posterior Nd:YAG capsulotomy in the study eye (if not already done) for all eligible participants followed by: Group 1- implantation of the OriLens device plus three sessions of low vision training; Group 2- three sessions of low vision training. In order to minimise the possibility of a placebo effect an equal number of low vision sessions will be given in each Group.

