8.3.2 Intervention adherence

Participants will be required to attend the low vision training sessions in order to adapt to the device. Adherence will be monitored by attendance at all low vision training sessions for both groups.

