8.3.3 Intervention discontinuation

Implantation of the OriLens device may not proceed if the participant has zonular instability or for any other reasons deemed appropriate by the surgeon. This will be at the surgeon's discretion.

The OriLens may be removed if required post-operatively. Removal of the OriLens is at the surgeon's discretion and may be requested by the participant.

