8.5 Participant Timeline

Eligibility will be determined at the screening visits. Surgery in Group 1 will take place at Day 0 with surgical review on days one and seven and study visits for both Groups at months one, three, six and 12. As the presence of the device is obvious to the casual observer, it will not be possible to mask assessors. Participants can also not be masked to the intervention. However, the final BCDVA measurement at 12 months will be duplicated by an additional observer independent to the trial and this measurement will be used for the primary analysis. BCDVA (primary outcome) will be measured with 4-meter ETDRS charts. Assessment at screening will include medical history, ophthalmic examination, confrontation visual field testing, visual acuity, reading speed, refraction, contrast sensitivity, assessment with x2.5 external telescope for distance and near vision, assessment for ocular dominance, binocular visual function, endothelial cell density, ocular coherence tomography (OCT) with volume scan, colour fundus photography, IVI, and EQ-5D-5L. Fundus fluorescein angiography (FFA) will be carried out in addition to OCT at baseline and only subsequently if clinically indicated as OCT cannot be performed post implantation of the device. The order of screening examinations will follow as per Figures 3 and 4, however, this may vary at site depending on the location of equipment. The detailed schedule is shown below in Table 2.

If all inclusion criteria are met at both screening visits, participants will be enrolled into the study. The required clinical information will be returned to the lead site (NICTU) and the study eye will be selected. The participant will be informed within 72 hours regarding which eye has been selected as the study eye and will be provided with a date to attend for Nd:YAG capsulotomy in the study eye, if not already done. After the participant has undergone the laser treatment, the Principal Investigator (PI) or designee will contact the CTU to determine group allocation. The participant will then be notified within 72 hours post laser treatment regarding group allocation.

Group 1 Care Pathway:

- Day 0: Surgery (surgical implantation of OriLens device)
- Day 1: Surgical review
- Day 7: Surgical review
- Assessments will be carried out at Months 1, 3, 6 and 12
- Low vision training at months 1, 3 and 12

Group 2 Care Pathway

- Day 0: No procedure

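### The per-protocol rule is liable to drop explanted participants from the implant arm only, so the supportive estimate could overstate the effect of receiving the device

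*Protocol*

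**What the plan says.** Section 10.6.1 states that "the primary analysis will be conducted on an intention to treat basis", whatever the adherence. It then adds a per-protocol comparison that "includes only those participants who completed the treatment originally allocated". The next sentence limits the mechanistic analysis to subjects "who were randomised to the intervention arm and who received the treatment originally allocated", using a different verb.

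The allocated treatments are given in section 8.3: "implantation of the OriLens device plus three sessions of low vision training; Group 2- three sessions of low vision training". Section 8.5 gives both groups the same schedule: "Low vision training at months 1, 3 and 12". Section 8.3.2 defines the only adherence measure: "Adherence will be monitored by attendance at all low vision training sessions for both groups".

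Section 8.3.3, headed Intervention discontinuation, covers two events that can happen only in the implant arm. Before implantation, "Implantation of the OriLens device may not proceed if the participant has zonular instability" or for other reasons at the surgeon's discretion. Afterwards, "The OriLens may be removed if required post-operatively", and the participant may ask for this. Section 8.7.4 says that after removal the participant goes back to standard care. The list of anticipated adverse events in section 11 includes removal of the device.

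**The concern.** A per-protocol set is chosen on events after randomisation, so it gives up the protection of randomisation. Here one selecting event is a result of the device itself. A device is likely to be taken out because of a complication, poor vision or dissatisfaction. If such participants leave the implant arm while an equally dissatisfied control who attends training stays, the comparison becomes successful implants against adherent controls.

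The per-protocol result will stand beside ITT in a trial whose participants cannot be masked (section 9.4). A reader may take agreement between the two as corroboration when part of that agreement, or a more favourable per-protocol figure, comes from the exclusion rule. The same would apply to quality of life if the per-protocol set is used there, because dissatisfaction is a route to removal.

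**Working it through.** **Does the rule drop removals?** Three features of the protocol point that way:
- Removal is provided for under a heading about discontinuing the intervention (8.3.3).
- It is followed by a return to standard care (8.7.4).
- Section 10.6.1 uses *completed* for the per-protocol set but *received* for the mechanistic set. If both verbs meant *implanted*, the change of word would serve no purpose.

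This is the stronger reading, but the text does not state it.

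**Inputs from section 8.6.** Implant arm gains 10 letters; control mean (SD) 1.94 (13.4); difference 10 − 1.94 = 8.06. The plan's sample size reproduces: n = 2 × [13.4 × (1.960 + 1.282) / 8.06]² = 58.1, so 59 per group; 59/0.9 = 65.6, so 66 per group and 132 in total. That calculation is sound and does not bear on this point; only its means are reused.

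**Assumed inputs, because the protocol gives none.** r is the share of the implant arm whose device is removed. m is their mean change at 12 months. Retained devices gain 10 letters, and everyone in the arm is implanted.

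- ITT difference = (1 − r) × 10 + r × m − 1.94
- Per-protocol difference with removals dropped = 10 − 1.94 = 8.06
- Excess = r × (10 − m)

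| r | m = 10: ITT (excess) | m = 1.94: ITT (excess) | m = −5: ITT (excess) |
|---|---|---|---|
| 2% | 8.06 (0) | 7.90 (0.16) | 7.76 (0.30) |
| 5% | 8.06 (0) | 7.66 (0.40) | 7.31 (0.75) |
| 10% | 8.06 (0) | 7.25 (0.81) | 6.56 (1.50) |
| 20% | 8.06 (0) | 6.45 (1.61) | 5.06 (3.00) |

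**Adding non-implantation.** Now ITT also falls because some participants never get the device, so the fair reference is the effect of receiving the implant. Assume 5% not implanted (mean 1.94), 10% removed and 85% retained.
- Removed eyes at −5: ITT = 0.85 × 10 + 0.10 × (−5) + 0.05 × 1.94 − 1.94 = 6.16. The complier average causal effect is 6.16/0.95 = 6.48, against 8.06 per protocol (ratio 1.24).
- Removed eyes at 1.94: ITT = 8.5 + 0.194 + 0.097 − 1.94 = 6.85. The complier effect is 6.85/0.95 = 7.21, against 8.06 (ratio 1.12).

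**Adding control exclusions for missed training.** Take r = 10%, m = 1.94 (ITT 7.25), and exclude 10% of controls with mean c. The retained control mean is (1.94 − 0.1c)/0.9.

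| c | Retained control mean | Per-protocol difference |
|---|---|---|
| −3.06 | 2.50 | 7.50 |
| 0 | 2.16 | 7.84 |
| 1.94 | 1.94 | 8.06 |
| 5 | 1.60 | 8.40 |

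Control exclusions can therefore shrink or widen the gap over ITT.

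**The case against.** A reader might infer that the per-protocol set certainly drops every removal, that controls face no exclusion at all, and that the estimate is therefore inflated. The protocol does not support that.

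- **Completion is undefined.** Someone implanted, trained at every session and explanted later could be counted as having completed. On that reading this mechanism vanishes. This stands as a limit on certainty, but it leaves two analysts free to build different sets.
- **Controls can be excluded too.** Training is part of the allocated treatment in both arms, and attendance is monitored in both. This stands: what controls lack is a counterpart to removal.
- **The direction is conditional.** No removal rate or post-removal acuity is given, and section 5.2 notes recipients who are unhappy despite measured gains. This stands in part. Those are people with the device in place; an eye explanted before month 12 has lost the magnification, so keeping the full 10 letters is the least plausible column of the table.
- **Crossover works the other way.** The device is CE marked (section 5.1). A control who obtained one and stayed in the set would raise the control mean and count against the device. This stands, though no crossover rate is given.
- **Detail belongs in the SAP.** Section 10.6.2 promises a SAP, which was not available here, and definitions of this kind are often left to it. But section 10.6.1 already fixes the rule, so the protocol's own wording is open to comment.

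**Conclusion.** The point holds as a weakness of a supportive analysis. The per-protocol rule is liable to select on a device-related event that can occur in one arm only. If removals occur and those eyes do worse than retained implants, the per-protocol difference exceeds the effect of receiving the implant.

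The size cannot be established from the protocol. Under the assumptions shown, and with no other exclusions, the excess over ITT is about 0.2 to 1.6 letters for 2% to 20% removal with removed eyes at the control mean. It reaches 3.0 letters in the most adverse case examined and is zero if removed eyes keep the full gain.

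It would be wrong to conclude that the trial's main result is biased: the ITT estimate is the same under every definition of the per-protocol set. Nor do the two verbs in section 10.6.1 contradict each other, since they define sets for different purposes.

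**What to change.** In section 10.6.1, replace or accompany the per-protocol comparison with a complier average causal effect estimate, with randomisation as the instrument and implantation as the treatment received. This keeps the randomised comparison. Its main assumption, that allocation affects acuity only through implantation, should be stated, since an operation begun but abandoned without implanting could strain it.

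If a per-protocol set is kept:
- count participants who were implanted and later explanted as having received their allocated treatment;
- treat controls who obtain a telescopic implant as not having received theirs;
- apply one training-attendance rule to both arms, and say how the third session counts, since it falls at month 12 with the primary assessment;
- label the result supportive only. This set still omits Group 1 participants who were never implanted, which is why the complier estimate is preferable.

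The cost is a few sentences of protocol or SAP wording and one CRF check for telescopic implants in controls, at visits where ophthalmic history is already taken. Non-implantation and removal requests are already recorded (8.7.4). The supportive estimate will probably be somewhat less favourable. It will also be less precise than ITT: with 95% implanted, the standard error grows by about 1/0.95 = 1.05.

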10.6.2 Statistical methods

The primary endpoint is the change from baseline of BCDVA at the 12-month time point in the study eye. The treatments will initially be compared using the independent t-test followed by a repeated measures analysis of covariance, adjusting for site, baseline BCDVA as a covariate and other covariates/factors where appropriate. Possible covariates/ factors will be discussed in the Statistical Analysis Plan (SAP) and may include size of scar, thickness of scar, and ocular dominance. Statistical diagnostic methods will be used to check for violations of the model assumptions and data transformations or non-parametric equivalents such as Mann-Whitney may be performed as appropriate. The primary data at 12 months are the BCDVA measurements by the independent assessor. The 12 month BCDVA data measured by the optometrist on the research team will be analysed as part of a sensitivity analysis.

The continuous secondary endpoints will be analysed in the same manner as the primary endpoint with an endpoint specific baseline covariate term included.

Analyses will be two-sided and tested at an a priori significance level of p=0.05. The primary time point has been defined as the 12-month time point. There is no adjustment for multiple testing at the different time points, as the primary outcome has been defined and prioritised.

For the mechanistic evaluation, descriptive statistics will be used to present the results. Also, the relationship between visual outcome and several factors (as discussed in Section 7.1) will be investigated using the independent t-test, 1-way analysis of variance, Pearson's correlation coefficient or non-parametric equivalents as appropriate depending on the scale of measurement of the factors.

Inter-rater reliability between the independent assessor and the optometrist on the research team will be tested for BCDVA at 12 months using the intra-class correlation coefficient.

Baseline characteristics, follow-up measurements and safety data will be described graphically and in tabular format using appropriate descriptive summary measures depending on the scale of measurement and distribution.

A detailed SAP will be written by the trial statistician prior to the final analysis.

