5.2 Rationale for the Study

This trial will evaluate the efficacy and safety of a new intraocular implantable device (OriLens) to improve vision in participants with severe AMD. In advanced AMD, there are no effective treatments to improve vision. Visual aids such as hand-held magnifiers or external telescopic lenses may provide modest visual improvement to some participants and only for some specific tasks. Patients with AMD often have co-existing cataract, but it remains uncertain whether surgery is useful as visual improvement after cataract surgery is very limited. Despite this, many patients are keen to undergo cataract surgery as they are anxious for any possible improvement, no matter how small.

Protocol Number, Version 1.0_FINAL_27.04.2016

Intraocular telescopic or magnifying devices have been tried in people with advanced AMD, and several uncontrolled reports have described improvement in visual function. However, evidence from randomised trials is not available. The OriLens has recently become available (6) offering a number of features, which would seem to be advantageous in comparison to other implants regarding their efficacy and safety. Intraocular magnifying devices were reviewed by NICE in 2008 (IPG272, 11). The appraisal concluded that these devices should be used under "Special Arrangements". A further planned NICE appraisal review in 2011 was abandoned due to lack of further evidence. The aim of this project is to investigate the efficacy, safety and cost-effectiveness of this device.

Although significant improvements in visual acuity in participants with intraocular magnifying devices have been reported, a number of participants remain unhappy with the device, in spite of measured improvement in visual acuity. The study also seeks to investigate participant ocular parameters which may impact on the outcome, either positively or negatively, of the implantation of these devices. We propose a number of research questions to try to understand this with a view to optimising participant selection, procedures and outcomes.

5.3 **Rationale for the Intervention**

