6 STUDY AIM AND OBJECTIVES

6.1 **Research Hypotheses**

Efficacy Evaluation: Implantation of the OriLens, a novel intraocular telescopic lens, will improve visual function and quality of life in participants with advanced AMD.

Mechanistic Evaluation: 1. To explore whether participant ocular parameters such as scar size, volume at site are associated with visual outcome and to assess the importance of Preferred Retinal Locus (PRL) and ocular dominance on outcomes. 2. To evaluate the role of binocularity and visual summation on participant-reported outcomes.

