7 STUDY DESIGN

7.1 Study Design

The project will be a multicentre randomised controlled trial which will evaluate the efficacy, safety and cost-effectiveness of a novel intraocular telescopic lens (OriLens). We will enrol participants with bilateral advanced stable AMD who have had previous cataract surgery (bilateral pseudophakia). Surgical implantation of the OriLens will be carried out within eight weeks of randomisation. Primary and secondary outcomes will be assessed at one, three, six and 12 months post randomisation.

Those who fulfil the inclusion criteria will be randomised equally (stratified by site) to one of two groups: Group One (Surgical Intervention) will undergo implantation of the OriLens device as a secondary surgical procedure in addition to usual standard of care; Group Two (Conventional Intervention- Control) will receive usual standard of care.

In addition, a number of participant specific parameters will be evaluated to assess the impact of these factors on participant outcomes. Specifically, the study will evaluate the following using data collected during the study.

- 1. Does the type, size and location of the scar/atrophy or the preferred retinal locus (PRL) have an impact on visual outcome?
- 2. Does implantation in the aiming dominant/non-dominant eye produce a better outcome?
- 3. Do participants who have good binocular function pre-operatively, find use of the telescopic device more difficult?
- 4. Do pre-operative binocular vision abnormalities impact on acceptance and use of the device?
- 5. Does implantation of the device cause a change in visual summation and does this impact on the tolerability of the device?

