8.7.4 Withdrawal of consent

Participants may withdraw or be withdrawn from the trial at any time without prejudice. In the event of consent withdrawal, participants will be asked for their permission to use the data already collected to date. If this permission is declined, any data collected to date on that participant will not be entered into the trial analysis. A withdrawal of consent form will be completed in the CRF defining further use of data.

All study investigators will be informed of the participant's withdrawal and they will not be contacted again with regards to the study. If the participant requests removal of the OriLens device, an appointment will be provided by the operating surgeon and the participant will be given the

opportunity to discuss the request for removal. The consultation will include discussion on reason for the request to have the device removed and the potential risks and benefits of removing the device. If removal goes ahead, the participant will revert to standard care treatment.

Withdrawal of consent, participant/PI request not to proceed with implantation of the OriLens, or participant/PI request to have the OriLens removed will be recorded on the CRF.

9 Methods: Assignment of interventions

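### Section 10.6.2 relates the binocularity factors to visual outcome, but the objective is participant-reported, and questions 3 to 5 on difficulty, acceptance, use and tolerability have no named direct measure

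*Protocol*

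**What the plan says.** Protocol section 7.1 lists five participant-level questions and states that "the study will evaluate the following using data collected during the study". Question 3 reads "Do participants who have good binocular function pre-operatively, find use of the telescopic device more difficult". Question 4 reads "Do pre-operative binocular vision abnormalities impact on acceptance and use of the device". Question 5 asks whether a change in visual summation affects how well the device is tolerated.

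Sections 6.1 and 6.3.2 divide the mechanistic work in two. Scar characteristics, preferred retinal locus and dominance are set against visual outcome or outcomes in general. The second part is "To evaluate the role of binocularity and visual summation on participant-reported outcomes". Section 8.4.2 repeats the binocularity item but says only outcomes, without naming the type.

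Section 10.6.2 gives the analysis. First, "For the mechanistic evaluation, descriptive statistics will be used to present the results". Then it adds that "the relationship between visual outcome and several factors (as discussed in Section 7.1) will be investigated", using t-tests, one-way analysis of variance, correlation or non-parametric equivalents. Section 10.6.1 restricts this analysis to participants randomised to the implant who received it.

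Section 5.2 gives the motive: "a number of participants remain unhappy with the device, in spite of measured improvement in visual acuity".

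**The concern.** The only dependent variable that section 10.6.2 names is visual outcome. Section 5.2 says that this part of the trial exists because acuity gain and satisfaction can part company. Sections 4.3.5 and 8.2.4 add a related failure: an implanted eye may be ignored or suppressed. A participant whose measured vision improves but who finds the device hard to use, or rejects it, counts as a good result in an analysis of visual outcome. If binocular status matters mainly for that kind of participant, the tests as written are poorly placed to show it.

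The stake is the stated purpose of the mechanistic work, which is better selection of participants. Data on difficulty and use that are not collected at the visits cannot be recovered by an analysis plan written before the final analysis.

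**Working it through.** The protocol gives no calculation for this point, so the check sets its sections side by side.

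**Step 1. What each question asks, against what section 10.6.2 tests.**

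| Section 7.1 question | Outcome asked about | Outcome named in 10.6.2 | Match |
|---|---|---|---|
| 1. Scar or atrophy, preferred retinal locus | Visual outcome | Visual outcome | Yes |
| 2. Dominant or non-dominant eye | A better outcome, type not given | Visual outcome | Compatible |
| 3. Good binocular function | Difficulty of use | Visual outcome | No |
| 4. Binocular abnormalities | Acceptance and use | Visual outcome | No |
| 5. Change in visual summation | Tolerability | Visual outcome | No |

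Three of five do not match. They are the three that belong to the binocularity and summation objective, for which sections 6.1 and 6.3.2 specify participant-reported outcomes.

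**Step 2. Are the predictors for questions 3 and 4 collected?** Yes. Table 2 places the orthoptic assessment, including binocular function, at Screening 2.

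**Step 3. Does the protocol name a direct measure of the outcomes asked about?** Table 2, the visit list in section 10.2.2 and the instruments in section 10.3 were searched.

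- Follow-up covers distance and near acuity, reading speed, contrast sensitivity, refraction, eye examination and adverse events, with fundus photography and specular microscopy at month 12. None reports difficulty, acceptance or use.
- The IVI (baseline, 6 and 12 months) is participant-reported, but it covers vision-related quality of life and not the device.
- The EQ-5D-5L is generic.
- The resource questionnaire covers services and privately bought vision aids. No item on the implant is described.
- Adherence in section 8.3.2 is attendance at training, not use of the device.

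**Step 4. Which indirect measures exist?** Section 8.7.4 says that a "participant/PI request to have the OriLens removed will be recorded on the CRF". The anticipated adverse event list includes removal and repositioning of the device. Removal or a request for it is a crude indicator of acceptance. Requests not to proceed with implantation are recorded too, but section 10.6.1 keeps people who were never implanted out of this analysis.

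**Step 5. Number of participants affected.** The sample size section gives 59 per group, inflated for attrition (read as 10%): 59 / (1 − 0.10) = 65.6, rounded up to 66. The mechanistic population is therefore at most 66. This figure only bounds the group concerned; the finding does not depend on it.

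**The case against.** There is a good case for a milder reading.

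- **Section 10.6.2 does not say that visual outcome is the only outcome.** Descriptive results are promised first, without a limit on the variable, and the tests are introduced as an addition covering several factors. This stands, and the participant-reported analysis in 6.1 and 6.3.2 is not cancelled. But the inferential analysis names one outcome, and it is not the one that the objective names.
- **Visual outcome is wider than acuity.** It can include near vision, reading speed and contrast. This also stands, and section 5.2 speaks only of acuity. These are still performance tests, not participant reports.
- **Table 2 is not a full list of CRF items.** The safety analysis tabulates a recent falls question that appears in neither Table 2 nor section 10.2.2. A device-use item could likewise sit in the CRF or trial manual. So the most that can be said is that the protocol names none.
- **The analysis plan could map the IVI to these questions.** It could, and that part might be left to it. But 10.6.2 states an outcome of its own, and what is measured at each visit has to be settled before follow-up.

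A reader might infer that questions 3 and 4 go wholly unanswered, or that acceptance is never examined. The documents do not support that. Removal requests and device-removal events are recorded, and the IVI is a plausible referent for participant-reported outcomes.

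**Conclusion.** The point holds in a limited form. The dependent variable named in section 10.6.2 does not match the participant-reported objective in sections 6.1 and 6.3.2 or questions 3 to 5 of section 7.1, and the protocol names no direct measure of difficulty, acceptance, use or tolerability. These three of five questions, in at most 66 participants, therefore rest on proxies that are indirect and unassigned. Removal captures only outright rejection, and the IVI is not specific to the device.

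The conclusion assumes that the CRF and trial manual hold no device-use item beyond what the protocol describes; if they do, the measurement gap closes and only the mismatch in 10.6.2 remains. It also assumes that a participant whose device is later removed still counts as having received the allocated treatment.

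The change should be made, but it does not threaten the trial. These analyses are descriptive or exploratory within the implant arm. The primary endpoint, the sample size and the comparison between arms are untouched.

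**What to change.** 1. In section 10.6.2, for questions 3 to 5, keep visual outcome and add (a) change from baseline in IVI total and subscale scores at 6 and 12 months and (b) removal of the OriLens or a request to remove it. This brings 10.6.2 into line with 6.1 and 6.3.2. In 8.4.2, specify which outcomes are meant for the binocularity item.
2. In Table 2 and section 10.2.2, add one short participant-rated item on difficulty and use of the device for the implant arm at the existing visits (months 1, 3, 6 and 12), unless the CRF already holds one; in that case, cite it. Hours of use per day would not suit a device that is implanted and not put on and taken off.

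Part 1 costs only wording and uses data already collected. Part 2 costs one or two CRF questions, with no new visit or procedure. The remaining weakness is that the part 1 measures are not device-specific, which is why part 2 is worth adding.
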